9.9.1 Primary Effect Analyses

Clinician Administered PTSD Scale-4 (CAPS-4)

The primary effect evaluation is the change from baseline to the end of stage 1 outcome timepoint (visit 12) in the CAPS-4 Global Severity score of PTSD (difference score).

9.9.2 Secondary Effect Analyses

The secondary effect analyses will be made comparing change from baseline (Baseline) to the end of stage 1 outcome timepoint (visit 12) of all the secondary measures except the PDS, following the same methodology used for the primary endpoint.

PTSD Diagnostic Scale (PDS) total scores will be analyzed in the same manner as the CAPS-4 global scale primary analysis.

Global Assessment of Functioning (GAF) total score will be analyzed in the same manner as the CAPS-4 global scale primary analysis.

Beck Depression Inventory-II (BDI-II) total score will be analyzed in the same manner as the CAPS-4 global scale primary analysis.

Pittsburgh Sleep Quality Index (PSQI) global scores will be analyzed in the same manner as the CAPS-4 global scale primary analysis.

9.9.2.1 Secondary Effect Analyses at Secondary Endpoints

Crossover Subject Analyses

Formal statistical comparisons between Stage 1 and Stage 2 scores may only occur if all three eligible participants enroll in Stage 2.

Long-term Follow-up

For the CAPS, PDS, BDI-II, GAF, and PSQI, the absolute changes in the measures from baseline to the long-term follow-up visit (one year post final experimental year) will be compared. The absolute changes in the measures from long-term follow-up to End of Stage 1 (full dose group) or long-term follow-up compared to End of Stage 2 (comparator group) will be compared.

9.9.3 Exploratory Analyses

Clinician Administered PTSD Scale-4 (CAPS-4)

- The percentage of subjects who achieve a 30% drop in CAPS-4 global score at the end of stage 1 endpoint (visit 12) will be an indirect measure of clinical significance. Descriptive statistics will be computed and displayed by Stage 1 treatment groups.
- The percentage of subjects who no longer meet PTSD diagnostic criteria according to the CAPS-4 at the end of stage 1 endpoint (visit 12) will be an indirect measure of clinical significance. Descriptive statistics will be computed and displayed by Stage 1 treatment groups.

PTSD Diagnostic Scale (PDS)

PDS total scores at baseline, after the third integrative session (Visit 7), the sixth integrative session (Visit 11) and at the end of stage 1 will be examined. Results will be used to examine the effects of each experimental session on self-reported PTSD symptom severity.

Clinician Administered PTSD Scale-4 (CAPS-4) and PTSD Diagnostic Scale (PDS)

PDS and CAPS scores will be correlated via Pearson's product moment correlation at baseline and the timepoint that the primary effect is measured to provide a comparison of a self-report measure with a clinician-administered measure of PTSD symptoms.

Primary and Secondary Effect Analyses Including 2 Lead-in Subjects Analyses detailed in Sections 9.9, 9.9.1 and 9.9.2 will be conducted in the same manner with inclusion of the 2 open label, lead-in subjects in the 125 mg treatment group.

9.9.3.1 Process Measures

Long-term Follow-up Questionnaire (LTFU Questionnaire)

The LTFU Questionnaire nominal variables will be described in terms of frequencies and percentages, while ordinal and non-normal continuous variables will be described using sample mean, standard deviations, and range.

Belief of Condition Assignment

In order to compare the therapists' and subjects' belief of treatment group to actual MDMA dose received in each blinded session, the number and frequency of correct guesses will be calculated and depicted by dose group and study role (subject and each therapist).

Reactions to Research Participation Questionnaire (RRPQ)

Frequency of response will be tabulated for 'reasons for participation' across Stage 1 treatment groups. Descriptive statistics will be computed for total scores for subscales and displayed by Stage 1 conditions.

9.9.4 Safety Analyses

The primary measure of safety will be the reporting of adverse events. The Adverse events considered are Treatment Emergent Adverse Events (TEAE) defined as those AE's that occurred after dosing and existing medical history diagnoses that worsened during the study. Verbatim terms on case report forms will be mapped to preferred terms and system organ classes using the MedDRA dictionary. For incidence reporting if a subject has more than one AE mapped to the same preferred term, that AE will be reported only once using the highest severity and closest relationship to study drug. Subject incidence of AEs will be displayed by treatment group by stage and by system organ class. AEs will also be summarized by severity and relationship to study drug. Subject incidence of SAEs by treatment group by stage will also be displayed. In addition to the listing of all AEs, a listing of SAEs and a listing of AEs leading to discontinuation of study drug will be included.

Summary tables of frequency listings of commonly reported AEs (Spontaneously Reported Reactions) mapped to preferred terms will be displayed during and after each experimental session by Stage 1 treatment group.

Columbia Suicide Severity Rating Scale (C-SSRS)

Suicidal ideation and behavior will be summarized according to suggestions made in the Columbia-Suicide Severity Rating Scale Scoring and Data Analysis Guide [2]. A positive response for suicidal ideation is counted when a subject answers "yes" to any one of the five suicidal ideation questions (Categories 1-5) on the C-SSRS, i.e. a score > 0 for suicidal ideation score. Serious suicidal ideation is a suicidal ideation score of 4 or 5. A positive response for suicidal behavior occurs when a subject answers "yes" to any one of the five suicidal behavior questions (Categories 6-10) on the C-SSRS, i.e. a score > 0 for suicidal behavior score. The number and percent of positive responses of Positive Ideation, Serious Ideation, and Positive Behavior will be tabulated by Stage I treatment group and time period. Compare lifetime serious suicidal ideation and positive behavior frequencies to cumulative frequencies anytime during the study until end of Stage 1 and Stage2.

Subjective Units of Distress (SUD)

Descriptive statistics for SUD scores will be calculated by Stage 1 treatment group and time period with counts and percentages.

Vital signs

Vital signs (heart rate, body temperature, systolic and diastolic blood pressure) will be summarized using descriptive statistics at baseline and at each post-baseline time point. Occurrences of systolic and diastolic blood pressure, heart rate, and body temperature readings above the pre-determined cutoff will be displayed with numbers and percentages by timepoint.

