5.2.2 Preparatory Psychotherapy Sessions (Visits 1, 2 and 3)

Subjects who do not complete all screening activities will not be enrolled. If all inclusion criteria and no exclusion criteria are met, eligibility will be confirmed with the subject during Visit 1. After eligibility is confirmed, the subject will be enrolled during Visit 1 and issued a subject number. The first preparatory session will take place after enrollment during Visit 1. Remaining preparatory sessions will be scheduled as described in the Time and Events table.

Upon enrollment, subjects who must refrain from taking a psychiatric medication will begin tapering off that medication following a time course appropriate for the medication given its half-life, with the first experimental session scheduled to occur after complete washout. The therapists will perform the C-SSRS once after medication washout but prior to the first experimental session. This may occur during a scheduled administration of the C-SSRS during the second preparatory session, or at an additional time appropriate to the medication washout.

a. Record preparatory sessions to audio and video. Subjects may receive

- copies of audio or video recordings from these preparatory sessions upon request.
- b. AEs and Medications will be recorded as described in Section 8.5 and 9.0 of the protocol from the time the subject is enrolled at Visit 1.
- c. The therapists will inquire about any possible changes in the subject's health to ensure that subject continues to meet eligibility criteria and if applicable, will confirm that the subject has appropriately tapered off of medications.
- d. The subject will undergo three preparatory sessions lasting at least an hour with the therapists, who will be a male and a female co-therapist team. The therapists will work with the subject to prepare him or her for MDMA-assisted psychotherapy. The therapists and subject will seek to form a strong working relationship with each other, and they will help the subject prepare for upcoming experimental sessions. Preparatory sessions will promote a safe space for confronting trauma-related memories, emotions and thoughts. Subjects will remain with the therapist team they begin with throughout the study.
- e. The subject and therapists will discuss goals for the experimental session and will review what will happen during the experimental session, following standard procedures and techniques discussed in the Sponsor's treatment manual.

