5.2.3 Experimental Sessions (Visit 4 and 8)

Subjects in Stage 1 will receive two double-blind experimental sessions of MDMA-assisted psychotherapy scheduled approximately 3-5 weeks apart, and subjects in the open label leadin and open label Stage 2 will receive two experimental sessions with the full dose of MDMA. Procedures for MDMA-assisted psychotherapy will remain the same across all sessions, and all procedures except the drug received will be the same.

- a. At least 24 hours prior to the first experimental session the subject will be randomized. The therapist team conducting the session will obtain the container assignment using a web-based randomization program prior to the session.
- b. On the day of the experimental session, the subject will arrive approximately 1-1.5 hours prior to drug administration.
- c. Confirm continuing eligibility by reviewing inclusion/exclusion criteria.
- d. Perform a urine drug screen. A positive drug screen will be reviewed by the investigator and may be cause for delaying drug administration to a later time, rescheduling the session to a later date, or withdrawing the subject from the study.
- e. If a woman is of childbearing potential, perform a urine pregnancy test. A positive pregnancy screen is cause for withdrawal from the protocol.
- f. If the subject continues to meet criteria and the subject reports that he/she followed appropriate rules and restrictions, the session will proceed.
- g. Review procedures for the experimental session with the subject.
- h. Record the entire session to video and audio. Subjects may receive a copy of audio or video recordings of their experimental sessions upon request.
- i. The session will last for approximately eight hours or longer, followed by an overnight stay at the study site.
- j. The subject will complete the C-SSRS approximately one hour to a half hour prior to drug administration.

Table 4. Schedule of procedures and measures for experimental sessions.

Approximate Time	Procedure or Action
9:00	Urine drug screen and pregnancy test. Subject acclimated to
0.45	environment, C-SSRS
9:45	Baseline BP, Pulse, Subjective Units of Distress Rating (SUD)
9:55	2 nd Baseline BP, Pulse, Body Temperature (BT), SUD
10:00	MDMA Administration, begin recording to audio and video
10:30	BP, Pulse
11:00	BP, Pulse, SUD, BT
11:30	BP, Pulse; Can administer optional supplemental dose
12:00	BP, Pulse, BT
12:30	BP, Pulse, SUD
13:00	BP, Pulse
13:30	BP, Pulse, BT
14:00	BP, Pulse, SUD

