8.0 Adverse Events

8.1 Adverse Events

An adverse event (AE) is defined as any untoward or unfavorable medical occurrence in a clinical research study participant, including any abnormal sign (e.g. abnormal physical exam or laboratory finding), symptom, or disease, temporally associated with the participants' involvement in the research, whether or not considered related to participation in the research. This definition includes concurrent illnesses or injuries and exacerbation of pre-existing conditions.

An *unexpected adverse event* is one that is not listed in the current Investigator's Brochure or an event that is by nature more specific or more severe than a listed event.

All AEs will be monitored by the therapists until resolution or, if the AE becomes chronic, a cause identified. If an AE is unresolved at the conclusion of the protocol, a clinical assessment will be made by the investigator and/or Medical Monitor as to whether continued follow-up of the AE is warranted.

The severity of events reported on the "Adverse Events" CRF will be determined by the investigator as:

- · Mild: No limitation in normal daily activity
- · Moderate: Some limitation in normal daily activity
- · Severe: Unable to perform normal daily activity

The relationship of the study treatment to an AE will be determined by the investigator based on the following definitions:

1. Not Related

The AE is not related if exposure to the investigational product has not occurred, or the occurrence of the AE is not reasonably related in time, or the AE is considered unlikely to be related to use of the investigational product, i.e. there are no facts (evidence) or arguments to suggest a causal relationship, or the AE is more likely related to the subject's pre-existing condition.

2. Possibly Related

The administration of the investigational product and AE are considered reasonably related in time and the AE could be explained by causes other than exposure to the investigational product.

3. Probably Related

Exposure to the investigational product and AE are reasonably related in time and the investigational product is more likely than other causes to be responsible for the AE, or is the most likely cause of the AE.

The relationship of the study treatment to an AE will be determined by the investigator.

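### SAP 9.9.4 does not tie worsening of existing diagnoses to dosing, so psychiatric worsening during the pre-dose medication taper is labelled treatment-emergent and counted under the subject's arm

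*SAP*

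**What the plan says.** SAP 9.9.4 states: "The primary measure of safety will be the reporting of adverse events". It then limits the events considered to treatment-emergent ones, "defined as those AE's that occurred after dosing and existing medical history diagnoses that worsened during the study". On presentation it says: "Subject incidence of AEs will be displayed by treatment group by stage and by system organ class". It also summarises events by severity and by relationship, and reports repeated events under one preferred term once, at the worst severity and the closest relationship. The Safety population in SAP 9.1 is everyone given any study treatment.

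Protocol 5.2.2 sets the timing of the taper: "Upon enrollment, subjects who must refrain from taking a psychiatric medication will begin tapering off that medication", "with the first experimental session scheduled to occur after complete washout". Item b of the same section has adverse events recorded "from the time the subject is enrolled at Visit 1". Protocol 5.2.3 item a adds: "At least 24 hours prior to the first experimental session the subject will be randomized". On causality, Protocol 8.1 says: "The AE is not related if exposure to the investigational product has not occurred".

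**The concern.** The sentence defining treatment-emergent events uses two different clocks. A new event must follow dosing. Worsening of a diagnosis already in the medical history need only fall within the study, and a subject is in the study from enrolment at Visit 1. Between Visit 1 and the first dose, subjects on psychiatric medication come off it. Worsening of PTSD or depression in that interval is a plausible result of stopping medication and cannot be a result of study drug.

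What is at stake is the count in the main safety table. Psychiatric worsening is one of the events a reader will look for first with this treatment. With arms of three and five, a single event of the wrong kind is visible in the percentages. SAP 3.0 also intends the data for a meta-analysis with other Phase 2 studies, so a wrong count could carry forward.

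**Working it through.** The documents give no event rate, taper rate or other figure on this point, so there is nothing of the plan's own to reproduce. The check is to follow one event from the taper to the table.

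1. **Is the window before the first dose?** Yes. Taper starts at enrolment (Visit 1) and washout is complete before the first session (Protocol 5.2.2). Table 2 places Visit 4 three to five weeks after Visit 1.
2. **Is it before randomisation?** Normally. Randomisation is at least 24 hours before the first session (Protocol 5.2.3), but no earliest time is given, so late washout could overlap with it. The two lead-in subjects are not randomised.
3. **Would the event be collected?** Yes, if psychiatric. Protocol 8.5 and Table 2 collect psychiatric-status events, serious events and events leading to withdrawal at Visits 1 to 3. Protocol 8.5 also allows collection of an exacerbation of a baseline condition. Events needing medical attention, and all other adverse events, start only at the first session.
4. **Does the subject have a qualifying diagnosis?** Yes. All have chronic PTSD, and a concurrent affective disorder other than bipolar 1 is allowed (Protocol 4.2.1).
5. **Does it meet the definition?** Yes, through the second limb, which asks only for worsening within the study.
6. **Does any later rule remove it?** No. The Safety population selects subjects who were dosed; it does not restrict when their events occurred. Grading as Not Related changes the relationship table, not the overall incidence table.
7. **What does the same-term rule do?** Suppose depression worsens severely during the taper, and mildly after dosing with a grade of possibly related. Both map to one preferred term. The subject is then reported once, as severe and as possibly related. The pre-dose severity is joined to a post-dose attribution, and the Not Related grade disappears.

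**Size of one such event.** The shift in incidence is 1/n:

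| Denominator | Shift |
|---|---|
| Active placebo, n = 3 | 1/3 = 33 points |
| Full dose, n = 5 | 1/5 = 20 points |
| Full dose pooled with lead-in, n = 7 | 1/7 = 14 points |
| Lead-in shown alone, n = 2 | 1/2 = 50 points |

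**How likely is at least one?** This needs a figure the documents do not give. Let q be an assumed chance that an at-risk subject has a history diagnosis worsen before dosing, and k the number at risk among the eight randomised. The probability is 1 − (1 − q)^k:

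| | q = 0.1 | q = 0.2 | q = 0.3 |
|---|---|---|---|
| k = 8 | 0.57 | 0.83 | 0.94 |
| k = 4 | 0.34 | 0.59 | 0.76 |
| k = 2 | 0.19 | 0.36 | 0.51 |

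**Does it favour an arm?** With the same q in both arms, the expected addition to incidence from pre-dose events alone is q in each, so the expected difference is q − q = 0. The realised difference can still be large. With all eight at risk and binomial counts of 3 and 5, the chance that these events alone separate the arms by 20 points or more is 0.47, 0.59 and 0.62 at q = 0.1, 0.2 and 0.3.

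**With the second limb tied to the first dose**, an event confined to the taper adds 0 subjects to either arm's treatment-emergent count.

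**The case against.** The best defence has four parts.

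- **Relationship grading.** A reader might infer that the plan attributes taper harm to the assigned dose. The documents do not support that: Protocol 8.1 grades a pre-exposure event Not Related, and SAP 9.9.4 tabulates relationship. What remains is that the overall incidence table still counts the event as treatment-emergent, and the same-term rule can overwrite the grade.
- **Listing of all events.** SAP 9.9.4 plans one, and with ten planned subjects a careful reader could pick out the pre-dose events. That limits the harm but does not correct the table.
- **Loose drafting.** The author may have meant worsening after treatment began. This is plausible, since the label is treatment-emergent and the first limb refers to dosing. But the text does not say so, and two programmers could build different tables from it.
- **Scope.** A reader might infer that worsening of any existing diagnosis is swept in. The wording would allow that, but non-psychiatric worsening before dosing would mostly not be collected unless it was serious or led to withdrawal. The practical problem is psychiatric worsening.

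The size is also open to challenge. The 1/n shifts would apply to any single misclassified event, and the arm denominators are planned ones. SAP 9.2 replaces dropouts, so more than three or five may be dosed, and SAP 9.9.4 does not say how lead-in subjects are grouped for adverse events. These limits stand.

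**Conclusion.** The point holds as a defect in a stated rule. Applied as written, SAP 9.9.4 labels psychiatric worsening during the taper as treatment-emergent and shows it under the subject's arm in the main safety table, before any study drug has been given.

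A reader might go further and infer that the safety comparison is biased towards one dose. That does not follow. For the eight randomised subjects, events before a blinded allocation are equally likely in either arm in expectation, so any imbalance is chance. SAP 9.9.4 specifies no formal test of adverse events, and SAP 7.0 treats any testing as exploratory. The absolute incidence in each arm may be overstated; the difference between arms becomes noisier.

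The shifts of 33 and 20 points illustrate one event at the planned arm sizes. Confidence is high for the gap in the wording. How often it would matter cannot be judged from the documents, because they do not say how many subjects taper or how often they worsen.

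**What to change.** In SAP 9.9.4, define treatment-emergent events as adverse events with onset after the first dose of study drug, together with pre-existing conditions that worsened after the first dose. Show adverse events and worsening between Visit 1 and the first dose in a separate pre-treatment row or listing, and apply the same-term rule only within the treatment-emergent set, so that pre-dose severity is not merged with a later event.

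The cost is a change of wording in the SAP and one listing, largely a subset of the listing of all events already planned. No new data are needed: SAP 9.2 already uses the first dose date when completing partial dates. Because that rule moves an event with an unknown day in the month of first dose onto the dose date, the visit at which such an event was recorded should decide whether it is pre-treatment. Clinical conduct does not change, and the taper events stay visible under the right label.

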8.5 Adverse Event Collection

All SAEs will be collected for the duration of the protocol. All SAEs which occur during the course of the trial, whether considered to be associated with the study drug or not, have to be reported within 24 hours of the investigator's awareness of their occurrence. All SAE reports should be faxed to the Sponsor. A fax number will be provided to the site in separate site-specific instruction for SAE reporting. In addition to the fax, the Clinical Investigator (CI) or designee should call the CRA during normal working hours and verbally inform the CRA of the SAE. During off hours or if medical advice is needed immediately please call the Sponsor Medical Monitor. An SAE reporting instruction with all contact numbers will be provided to the site prior to study start.

Medical Monitor

[name]

Email: [contact] [contact]

[contact]

Study Monitor contact information will be provided in a separate contact list.

Adverse events that will be collected for the duration of the protocol are:

- All SAEs will be collected through termination.
- All Adverse Events and spontaneously reported reactions will be collected on the day of drug administration and for seven days after each experimental session.
- Events requiring medical attention will be collected from the first experimental session through the subject's last 2-month follow up.
- Events related to planned treatments or physician visits for baseline conditions collected in the Medical History will not be collected unless there is an exacerbation of the condition.
- Any Adverse Event leading to withdrawal from the protocol will be collected throughout the study.
- All AEs related to changes in psychiatric status will be collected throughout the study.

A Memory aid card will be provided to the subject on the last visit prior to the 12 month follow up to record information on medications taken to treat SAEs, AEs leading to withdrawal and psychiatric AEs during the period between the end of Stage 1 or end of Stage 2 and the 12 month follow-up evaluation. The memory aid card will not be collected, but information from the card will be used to aid the subjects in providing information to the investigator. This information may be collected by phone.

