4.3 Safety Objectives

The safety objectives of the study are to monitor and assure safety of subjects during and after the experimental sessions by assessing physiological effects, psychological distress, adverse events, spontaneously reported reactions and suicidality.

- Suicidality will be assessed with the Columbia Suicide Severity Rating Scale (C-SSRS) during visits prior to experimental sessions, twice during experimental sessions, and several times after each experimental session, with comparisons made between subjects in each condition.
- Subjective Units of Distress (SUD) scores and vital signs including blood pressure, heart rate and temperature will be measured during each experimental session, and results will be compared between groups.
- Serious adverse events, adverse events and spontaneously reported adverse events ("reactions") will be collected during the study according to Section 8.5.

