7.0 Sample Size and Power Considerations

This study is a pilot investigation intended to gather preliminary data on the safety and effect of MDMA-assisted psychotherapy in ten subjects with chronic, treatment-resistant PTSD. Because of their exploratory nature, pilot studies are often not powered for detecting the desired effect. Because it is a pilot study in a small sample, results will be used to collect effect size estimates for statistical power calculations for adequately powered subsequent studies. Any significance testing will be considered exploratory.

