9.0 Analyses

In general, nominal variables will be described in terms of frequencies and percentages and analyzed using chi square analysis. Although the protocol plan specifies parametric t-tests and ANOVAs, the small group sizes (n=3 and n=5) make it a challenge to statistically assess the effectiveness of the treatment. Therefore, this statistical analysis plan acts to amend the data analysis plan in the protocol.

Clinical data will be presented in tabular format. Data not subject to analysis according to this plan will not appear in any tables or graphs, but will be included in the data listings. Analyses will be carried out with SAS Version 9.3 or higher. Selected results may be presented graphically using standard graphical software.

Post-hoc exploratory analyses not identified in this SAP may be performed to further examine the study data. These analyses will be clearly identified as such in the final clinical study report.

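### The one C-SSRS comparison spelled out in SAP 9.9.4 does not use the pre-drug baseline of SAP 9.5, so unless nobody is positive before dosing it generally does not identify who is new or worse afterwards

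*SAP*

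**What the plan says.** SAP 9.5 sets two C-SSRS reference points. The pre-enrollment assessment gives lifetime history. The assessment at preparatory session 2, or the V4 pre-drug assessment if that one is missing, gives the baseline.

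SAP 9.9.4 then defines positive ideation, serious ideation and positive behavior. For the middle one, "Serious suicidal ideation is a suicidal ideation score of 4 or 5". Counts and percentages of all three "will be tabulated by Stage I treatment group and time period". One comparison follows: "Compare lifetime serious suicidal ideation and positive behavior frequencies to cumulative frequencies anytime during the study until end of Stage 1 and Stage2". The C-SSRS text never mentions the 9.5 baseline. In the same section, vital signs are summarized at baseline and at each later time point. The C-SSRS summary is also said to follow suggestions in a cited scoring guide.

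SAP 4.3 makes suicidality a safety objective, "with comparisons made between subjects in each condition".

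**The concern.** The safety question is whether suicidality appears or worsens after dosing, and whether that differs by dose. The stated contrast fits this question poorly in three ways.

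- It sets lifetime history against study time. Nothing limits study time to the period after dosing, although the C-SSRS is given on study before the first dose: at V2, after any medication washout, and shortly before drug at V4 (Protocol 5.1.2 and 5.2.3; Table 2). On that reading, two subjects with a lifetime history, one positive only during a taper and one positive only after drug, look the same.
- It covers serious ideation and behavior only, so a rise within scores 0 to 3, or from 4 to 5, does not register.
- It names no dose group. If the Stage 2 count runs on from Stage 1, it also adds open-label full-dose time to comparator time for up to three crossover subjects. If the sentence means two separate cut-offs, the Stage 1 count is free of this.

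The C-SSRS is the instrument planned for this objective. SAP 9.0 and 9.10 treat analyses added later as post-hoc, so a display of change is best specified before unblinding.

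**Working it through.** The documents give no C-SSRS rate or test, so there is no plan figure to reproduce. The check is what the reported totals can identify.

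**Inputs.** Arms of n = 5 (full dose) and n = 3 (active placebo) come from SAP 6.0. Score ranges and flags come from SAP 9.9.4. Each subject is coded 0/1 for lifetime (l), pre-dose (b, with V2 and V4 pre-drug taken as one status) and post-dose (p). It is assumed that b ≤ l: anyone positive at baseline has a lifetime history. New means p = 1 and b = 0.

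**The stated contrast.** It reports L (the number with l = 1) and S (the number positive in the study).

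- If S counts b or p: at most S subjects are new (all have b = 0). At least max(0, S − L) are new, because only subjects with a lifetime history can have b = 1.
- If S counts post-dose assessments only, the bounds are the same.
- The number new is therefore fixed only when L = 0 or S = 0.

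| | n = 5 | n = 3 |
|---|---|---|
| Possible (L, S) pairs, (n+1)² | 36 | 16 |
| Number new not fixed (L ≥ 1 and S ≥ 1), n² | 25 | 9 |
| Number new fixed | 11 | 7 |
| Pairs with S < L (an apparent fall) | 15 | 6 |
| Falls with S ≥ 1, each fitting any number new from 0 to S | 10 | 3 |

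Without the assumption b ≤ l, and with S counting b or p, the minimum is 0 whenever S ≥ 1. The number new is then not fixed in 30 of 36 and 12 of 16.

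**Example.** Lifetime 3/5, in study 2/5. If both in-study positives occurred at V2, none is new. If one occurred at V2 and the other only after dosing, one is new. If both occurred only after dosing, two are new. The contrast prints the same figures each time.

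**The by-period table.** With B positive at baseline and P positive at a later period, the number new lies between max(0, P − B) and min(P, n − B). It is not fixed when B and P are both between 1 and n − 1: 4 × 4 = 16 of 36 pairs for n = 5, and 2 × 2 = 4 of 16 for n = 3. When B = 0 it always equals P.

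**Worsening.** Ideation 0 to 5 allows 15 rises. The serious flag is unchanged in 7 of them: six within 0 to 3, plus 4 to 5. Four (1 to 2, 1 to 3, 2 to 3 and 4 to 5) change neither the positive flag nor the serious flag, so the by-period table does not show them either.

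**The case against.** The strongest reply is that one sentence is being judged alone. The sentence before it gives counts by dose group and period, which is a display between conditions, and baseline is probably one of those periods. Treatment-emergent events include those "that occurred after dosing and existing medical history diagnoses that worsened during the study". Protocol 8.5 adds: "All AEs related to changes in psychiatric status will be collected throughout the study". Under SAP 9.0, data not analyzed "will not appear in any tables or graphs, but will be included in the data listings", and with ten subjects a listing shows individual courses. This stands as partial cover. It falls short because period totals fix the number new only in some cases, two flags miss some rises, and adverse events depend on someone reporting an event.

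Second, Exclusion Criterion 10 keeps out people at serious suicide risk, so having nobody positive for serious ideation or behavior before dosing is plausible. In that case S equals the number new, and the period table gives the number new at each period. This also stands. A reader might infer that the contrast can never show change after dosing. That is too strong: 11 of 36 and 7 of 16 pairs do fix the number.

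Third, study time might be meant as post-baseline or post-dose time. If it means post-dose time, the 25 of 36 and 9 of 16 do not change.

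Fourth, the cited scoring guide may already call for a shift from baseline. It is not in the documents, so this stays open; the SAP text itself does not state one.

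Last, the remedy has an imbalance of its own: a maximum over many post-dose assessments set against one baseline assessment favours an apparent rise. This is correct, and the fix has to allow for it.

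**Conclusion.** The point holds in limited form. SAP 9.9.4 is not silent on suicidality during the study, but the one contrast it spells out does not use the 9.5 baseline. Unless no dosed subject is positive before dosing, that contrast generally leaves the number new or worse after dosing unidentified. The counts rest on binary status, V2 and V4 pre-drug taken as one, and b ≤ l. They count possible tables and must not be read as the chance of a misleading result.

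A reader might also infer that the contrast is biased towards reassurance, since a lifetime is set against months of study. The documents do not support a direction. The longer lifetime window and Exclusion Criterion 10 favour an apparent fall, while counting pre-dose and Stage 2 assessments raises the in-study total. No size or direction of bias is claimed.

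The matter is minor: the analysis is descriptive, has no decision rule, and sits in a ten-subject pilot where "Any significance testing will be considered exploratory". It is worth changing because the change is cheap and serves a stated safety objective.

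**What to change.** Keep the lifetime comparison as context. Add, as the main C-SSRS comparison, a within-subject shift display by dose group (25 mg, 125 mg, and the two lead-in subjects separately):

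- **Rows:** 9.5 baseline ideation category (0 to 5) and any behavior, with the V4 pre-drug value alongside so that a rise between V2 and dosing is not counted as post-dose.
- **Columns:** maximum post-dose ideation category and any behavior, from first dose to V12.
- **Definitions:** new is absent at baseline and present after dosing; worse is a higher ideation category than at baseline.
- **Unequal looks:** read the display between dose groups, and show the category at each period or at V12 beside the maximum.
- **Stage 2:** show V14 post-dose to V22 separately, against its own pre-dose reference. Table 3 schedules the C-SSRS at V13 and at the start of V14.

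Add a note that second-integrative-session scores reach the CRF only when the therapists see an increase (Protocol 5.1.2), so stable positives there may be missed. In SAP 9.5, reconcile the two visit numbers given for preparatory session 2 (visit 2 and visit 3) with Table 2 footnote H, which places it at V2.

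The cost is some SAP wording and one small display from data already planned. The drawbacks are very small counts, overlap with the listings, and the unequal number of looks before and after dosing.
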